### Supplemental Imaging at Duke

To establish the breast imaging repository, each radiology center will be contacted to obtain CDs of all screening and diagnostic breast imaging exams (standard clinical process for receiving outside radiologic imaging exams) of women enrolled in EMPOWER- I and EMPOWER-II. The data (demographics, cancer type, date of diagnosis, age at diagnosis, treatment information) from the CCSS and EMPOWER Studies will be used to annotate the repository. The quality of all imaging studies added to the repository will be evaluated. A deep-learning segmentation method will be applied to optimize comparability between imaging studies.

## EMPOWER-II

To characterize mammographic breast density, a clinical and a semi-automated reading will be done. Cumulus, a validated semi-manual, semi-automated, standard computer-assisted thresholding software program, will also be used to estimate the total area and dense area of the breast from which % mammographic density is calculated (dense area/total area x 100). Findings will be compared to a non-cancer population of women who have screening mammograms at Duke. The EMPOWER survivors will be matched 1:3 to the non-cancer population, matched for age at study (within 2 years), calendar year of mammogram, race/ethnicity (white, non-Hispanic; African American, non-Hispanic; Hispanic; Asian; other), and menopausal status (pre-menopausal, post-menopausal).

A BPE (minimal, mild, moderate, marked), will be assigned to each MRI reviewed. BPE will also be measured by a fully automated computer algorithm developed by Duke Radiology collaborators. Findings will be compared to a non-cancer high-risk population of women who have screening breast MRIs at Duke (current repository with 900+ MRIs). The EMPOWER survivors will be matched 1:2 to the non-cancer population, matched for age at study, calendar year of mammogram, race/ethnicity, and menopausal status.

The Breast Cancer Surveillance Consortium's publicly available data on breast density will be used to confirm our findings in cases where the quality of images may be inadequate or when there is an inadequate number of non-cancer controls for the matching.

### 5.0 Data Collection:

The data collection planned for this study will be obtained from the Eureka app, mail, and telephone-based self-report questionnaires and medical record report (breast MRI and/or mammogram reports).

#### Supplemental Imaging

Duke's source of research material will be a limited data set placed in a breast imaging repository. The data will have encrypted identifiers and will be used specifically for research purposes.

The Duke EMPOWER Breast Imaging Repository will create a custom data collection and management system which collects information on patient demographics, medical history, breast imaging results, and pathology outcomes.

### 5.1 Primary and Secondary Outcomes:

The following items were developed in 'Mammography and High-Risk Survivors of Pediatric Cancer' (R21 CA106972; PI: [name]) and refined for EMPOWER-I (R01CA134722).

- Breast MRI practices: Items that characterize breast MRI practices, including a differentiation between screening and diagnostic breast MRI and barriers to having an MRI.
- Mammogram practices: Items that characterize mammogram practices, including a differentiation between screening and diagnostic mammography and barriers to having a mammogram.
- Ascertainment of the primary and secondary breast cancer surveillance outcomes: The primary outcome will be a self-reported breast MRI and mammogram. If a survivor reports that she has had a breast MRI and/or a mammogram, she will be asked the contact information for the imaging center. We will then contact the imaging center, provide the signed medical record release form (from enrollment), and request a faxed copy of the imaging report(s).
- Descriptive data on physician visits, abnormal imaging studies, biopsies and cancers: In the end-of-study survey, participants will be asked to describe all medical visits during the study period, including routine non-procedure breast-related visits. Women who have had a mammogram and a breast MRI or ultrasound will be asked if they had an abnormal imaging study and the follow-up procedures for this imaging study. As per CCSS standards, if a woman reports a breast cancer, we will seek copies of the pathology and operative reports and provide this information to the CCSS Pathology Center.

## EMPOWER-II

### 5.2 Mediating and Moderating Variables:

Items designated with an asterisk were developed in the ‘Mammography and High-Risk Survivors of Pediatric Cancer’ and refined for the EMPOWER-I Study. In EMPOWER-II, we will also include measures of patient activation and self-efficacy.

- Patient Activation Measure (PAM): measures patient activation and includes: believing one has an active role to play, having the confidence and knowledge to take action, taking action, and staying the course under stress.
- Knowledge of breast cancer surveillance recommendations: determines the level of knowledge regarding the recommendations for breast cancer surveillance and the benefits and other considerations of screening.
- Barrier scales: elicits a rank order of the most relevant and important barriers of breast MRI and those associated with mammogram, for those women who did not obtain the recommended screening.
- Pros and Cons of Breast MRI and Mammography: [name] and colleagues operationalized the concept of barriers and facilitators in the Pros and Cons of and Mammography instrument. In EMPOWER-I, with the assistance of [name], we developed and tested the utility of the Pros and Cons of Breast MRI instrument.
- Family history of breast cancer
- Attitudes towards breast cancer screening / Risk perception and health beliefs: will assess both general preventive health beliefs and breast cancer specific health beliefs, including breast cancer risk perception.
- Intention for engaging in breast surveillance and Communication with PCP about breast cancer surveillance: will assess whether women scheduled a visit with their PCP, their intention for surveillance, if they discussed breast cancer screening with their PCP, and the outcome of this discussion.
- Affect: will be measured using the adapted and shortened version of the Positive Affect Negative Affect Scale (PANAS). We will focus on emotions related to managing health.
- Future breast screening intentions: future plans for breast MRI and mammogram will be included, “When do you plan to have a breast MRI / mammogram in the future?” with the following options: within the next 6 months, in 6 months to 1 year, in 1-2 years, in 3-4 years, in 5 or more years, when my doctor recommends, when I have a symptom, not planning to have one, don’t know.
- Self-Efficacy: measures confidence in discussing breast surveillance with the PCP and obtaining the recommended screening using items developed by Champion and colleagues.

### 5.3 PCP Variables:

We will administer a baseline and end-of-study survey of the PCPs of women in EMPOWER-II. For this survey, we have modified a survey that we assisted [name] in developing as part of her career development award (K07CA134935; PI: [name]; Co-Mentor: [name]). Items within the survey include:

- Demographics: age, gender, years in practice, practice setting
- Past experience and comfort level: number of adult survivors of childhood cancer seen in last five years (categorical), frequency of receiving an SCP (categorical), comfort level with caring for survivors of three cancer types (Likert scale), and familiarity with available guidelines (Likert scale).
- Knowledge: Using a hypothetical vignette of a 29-year old female patient treated for Hodgkin lymphoma with chemotherapy and chest RT we will ask questions about screening for thyroid dysfunction, breast cancer, and cardiac dysfunction.

### 5.4 Economic Measurements:

In the proposed study, we will capture information regarding the replication costs of the intervention and health services resulting from the intervention. For the replication costs, the dollar amount will be determined per participant, for the materials, postage, PopSockets, and notifications/app messaging/mobile data use will

## EMPOWER-II

be determined per participant. To determine the health services resulting from the intervention, we will survey participants at the end-of-study measurement regarding their use of specific health care services (routine or acute medical visit unrelated to breast cancer screening, non-procedure breast-related medical visit). We will collect a copy of all breast imaging studies from the imaging facility. In addition, women reporting a breast biopsy or breast surgery will be asked to provide the contact information of the physician/medical facility so that we can obtain a copy of all breast surgical procedures. This strategy has been successfully employed in other CCSS studies, including EMPOWER-I.

### 5.5 Insurance Coverage and COVID-19 Impact Phone Survey:

After completion of the end of study survey, participants in the PA and PA+PCP groups will be contacted by phone to invite them to participate in a voluntary brief phone survey that will cover topics related to participant insurance coverage, COVID-19, and how these issues may have impacted their engagement in the EMPOWER intervention. All participation will be voluntary and participants will not receive additional compensation if they choose to participate in this additional study component.

## 6.0 Statistical Analyses

The primary analysis involves comparing the proportion of women with a self-reported breast MRI and mammogram in each intervention arm to C. In EMPOWER-I, we used self-report of the imaging studies. We also sought to obtain medical record (fax) confirmation of the self-reported imaging studies. We were successful in obtaining the proper reports for 85.7% of the participants. However, for the remaining 14.3%, we were unable to confirm the study due to lack of information provided by the participant regarding the imaging facility, the imaging facility being unable to locate records and the facility sending only partial information, despite multiple attempts to collect the data. Importantly, the findings were not substantively different when we repeated the analysis including only women with a fax-confirmed imaging study. Stratifying on the randomization strata, differences in these proportions will be estimated with stratum-adjusted proportions calculated using the weighted average of the stratum-specific differences and accounting for the sampling scheme. The Cochran-Mantel-Haenszel test will be used to test for differences between (1) PA and C, and (2) PA+PCP and C in an intent-to-treat analysis where women who do not complete the end-of-study assessment will be counted as not having had a breast MRI and mammogram. We will also perform a secondary analysis of women with a fax-confirmed imaging study. Based on EMPOWER 1 results, we do not expect results to differ based on race/ethnicity, but will verify this result here. The analytic methods for the secondary objectives will be the same as for the primary objective, using the Cochran-Manetel-Haenszel test to examine differences between the interventions (PA, PA+PCP) on breast cancer surveillance rates (breast MRI + mammogram) and on rates of each individual surveillance test.

To explore moderating factors that may be associated with obtaining a breast MRI and a mammogram, we will use mixed effects models. The mixed model is  $\mathbf{Y}_i = \mu(\mathbf{X}_i, \alpha, \mathbf{Z}_i, \mathbf{b}_i) + \mathbf{e}_i$  where for participant  $i$ ,  $\mathbf{Y}_i$  is the response vector capturing whether the participant had a breast MRI and mammogram,  $\mathbf{X}_i$  is a fixed effects design matrix that includes indicators for treatment group, randomization strata, assessment time (baseline and end-of-study), potential confounders, and moderator variables,  $\mathbf{Z}_i$  is a design matrix for the random effects that would allow random subject deviations from the population average response,  $\alpha$  contains the fixed effects regression coefficients,  $\mathbf{b}_i$  contains the random effects coefficients,  $\mathbf{e}_i$  is the vector of error terms, and  $\mathbf{b}_i$  and  $\mathbf{e}_i$  are normally distributed with means of zero. We will test whether variables significantly moderate having a breast MRI or mammogram by testing whether the regression coefficients associated with these variables are significantly different from zero. Further, by including interaction terms between potential moderating variables and the treatment group indicator, we will test whether the effectiveness of the intervention differs by the moderating factors.

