### 6.1 Missing Data

Every effort will be made to minimize missing data and participant drop-out, both among the women and their PCPs. The primary analysis is an intent-to-treat analysis and will include all women who are randomized to the study regardless of whether they complete the end-of-study assessment (participants who drop out will be counted as failures in this analysis). Secondary analyses will include exploratory comparisons restricted to women who complete the end-of-study assessment. If potential moderating and mediating factors are missing, we will use multiple imputation. We will explore missing patterns among the PCPs and may consider using multiple imputation if it is warranted.

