### 6.2 Sample Size and Power

The primary aim involves two pair-wise comparisons of equal importance. For each comparison, we fix the probability of a Type I error at 0.025 in order to maintain the overall probability of a Type I error at 0.05. We powered the study to detect a difference of 20% for each pair-wise comparison assuming equal randomization to each of the three arms and that the proportion of women in the control group who will have a mammogram and an MRI will be approximately 10% based on our previous work. Table 1 shows the power we expect to have using two-sided Mantel-Haenszel tests and indicates that we should have sufficient power to detect a clinically meaningful difference even if the proportion of women in the control arm with the primary endpoint is somewhat higher than we expect. The power calculation of the Cochran-Mantel-Haenszel tests assumes a common risk ratio among the strata, that all strata generate the same proportion for the control arm and intervention arm.

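### As worded, the fax-confirmed secondary analysis is limited to a set defined by the outcome; its denominator should be all randomised women

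*Combined protocol and SAP*

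**What the plan says.** - Outcome (section 5.1): "The primary outcome will be a self-reported breast MRI and mammogram".
- Primary analysis set (section 6.1): it "will include all women who are randomized to the study regardless of whether they complete the end-of-study assessment", and sections 6.0 and 6.1 both count non-completers as failures.
- Who can be confirmed (section 5.1): "If a survivor reports that she has had a breast MRI and/or a mammogram, she will be asked the contact information for the imaging center". The centre is then contacted for the report.
- The check (section 6.0): "We will also perform a secondary analysis of women with a fax-confirmed imaging study". No denominator is given, nor any rule for women whose report was not obtained or who had no imaging. The text does not say whether one confirmed test is enough or both are needed.
- The precedent (section 6.0): in EMPOWER-I, "We were successful in obtaining the proper reports for 85.7% of the participants", and "the findings were not substantively different when we repeated the analysis including only women with a fax-confirmed imaging study".

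**The concern.** Having imaging is what the interventions are meant to change. An analysis set that a woman can enter only by having imaging, and having it confirmed, is therefore formed after randomisation by the outcome itself, and the arms within it are no longer comparable.

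This matters because the primary outcome is self-reported, no blinding is described, and the in-app surveys in Appendix II repeatedly ask women in the active arms whether they have had both tests. If over-reporting differs by arm, the record-based analysis is where it should show. The completers-only analysis in section 6.1 addresses dropout, not accuracy of report. A check carried out on the literal set could neither support nor contradict the primary result.

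**Working it through.** **Inputs from the documents.** 320 women randomised 1:1:1 (sections 3.0 and 3.2), so 320/3 = 106.7, about 107 per arm. Control 10%, intervention 30%, two-sided tests with alpha 0.025 per comparison (section 6.2: "we fix the probability of a Type I error at 0.025 in order to maintain the overall probability of a Type I error at 0.05"). Confirmation 85.7% (section 6.0).

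**Assumptions.** The share of women with one test only is not given, so a range is shown. The 85.7% is stated per participant and its denominator is unclear; here it is applied equally to all women with imaging, in both arms.

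**The plan's own figure.** Power = Φ[(d − 2.241·s0)/s1], where d is the difference, s0 the pooled and s1 the unpooled standard error. For 10% versus 30% this gives 90.0% at 97 per arm without continuity correction and 90.1% at 107 per arm with it, against 90% in Table 1. At 107 per arm without correction it is 92.8%, the like-for-like reference below.

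**Literal reading, both tests confirmed.** Every included woman is a success: 100% versus 100%.

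**Literal reading, at least one test confirmed.** With b the both-test rate and s the one-test-only rate, the analysis estimates b/(b + s) in about 106.7 × 0.857 × (b + s) women per arm. With b = 10% versus 30%:

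| s, control / intervention | Control | Intervention | Difference (points) | Women | Power |
|---|---|---|---|---|---|
| 10% / 10% | 50% | 75% | 25 | 18 vs 37 | 35% |
| 15% / 15% | 40% | 67% | 27 | 23 vs 41 | 43% |
| 15% / 30% | 40% | 50% | 10 | 23 vs 55 | 7% |
| 20% / 45% | 33% | 40% | 7 | 27 vs 69 | 5% |
| 10% / 30% | 50% | 50% | 0 | 18 vs 55 | no difference |
| 25% / 10% | 29% | 75% | 46 | 32 vs 37 | 96% |

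The true difference is 20 points in every row.

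Unequal change in one-test-only uptake is realistic. In EMPOWER-I (section 1.0) mammography was 39.8% versus 19.6%, while MRI was 18.7% versus 16.4%.

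**All randomised women, unconfirmed counted as not done.** 0.10 × 0.857 = 8.6% and 0.30 × 0.857 = 25.7%, a difference of 17.1 points. At 107 per arm, s0 = 0.0515 and s1 = 0.0502, so power = Φ[(0.1714 − 2.241 × 0.0515)/0.0502] = Φ(1.11), about 87%.

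**Excluding only reporters who could not be confirmed, keeping women without imaging.** 0.0857/(1 − 0.10 × 0.143) = 8.7% and 0.2571/(1 − 0.30 × 0.143) = 26.9%, a difference of 18.2 points.

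**Which reading fits EMPOWER-I?** The self-report result was 39.8/19.6 = 2.03 as a ratio.

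- Only women with a confirmed mammogram: 100% versus 100%, ratio 1.0.
- Only women with either test confirmed: if the tests are independent, 0.398/(1 − 0.602 × 0.813) = 78% versus 0.196/(1 − 0.804 × 0.836) = 60%, ratio 1.30. With no overlap, 0.398/0.585 = 68% versus 0.196/0.360 = 54%, ratio 1.25. With full overlap in both arms the ratio is 1.0. The maximum, 1/0.544 = 1.84, needs full overlap in the intervention arm and none in control.
- All women, unconfirmed counted as not done: 34.1% versus 16.8%, ratio 2.03.
- Only unconfirmed reporters dropped: 36.2% versus 17.3%, ratio 2.09.

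**The case against.** The strongest reply is that the sentence is shorthand. Section 6.0 opens by comparing the proportion of women who report both tests, where that phrase is the numerator; the fax-confirmed sentence can be read in parallel, as a confirmed numerator over all randomised women. The EMPOWER-I arithmetic supports this: a repeat that was not substantively different from a ratio of 2.0 fits the two versions that keep women without imaging, and fits a strict subset poorly.

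That stands as evidence about intent. A reader might infer from "when we repeated the analysis including only women with a fax-confirmed imaging study" that the authors mean to analyse confirmed women only; the reported EMPOWER-I result does not support that inference. But the phrase is literally restrictive, no section states the wider denominator, and the two usable versions give different estimates (17.1 versus 18.2 points) with nothing to choose between them.

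A reader might also infer that the check would reverse the sign of a real effect. At the planned 10% versus 30%, that requires one-test-only uptake to rise more than threefold. It can occur with a smaller effect (10% versus 20% for both tests, with assumed one-test-only rates of 16% and 40%, gives 38% versus 33%), but the documents give no such rates.

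A further objection concerns the remedy. Section 6.0 names missing facility information from participants as one reason confirmation failed. Appendix II places in-app prompts for facility name and address under the intervention messages; the control list has none before the end-of-study survey. Confirmation may therefore be higher in the intervention arms, and counting unconfirmed tests as not done could favour them. For example, equal true rates of 20% with assumed confirmation of 80% versus 95% give 16% versus 19%. This stands.

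**Conclusion.** The concern holds for the sentence as written. Followed literally, the analysis is either degenerate (100% versus 100%) or an estimate of both tests given any imaging. In the cases shown, the latter turns a true 20-point difference into 0 to 46 points, and in the four cases with a difference of 7 to 27 points power is at most 43%. Those figures rest on assumed one-test-only rates and on equal 85.7% confirmation; the degenerate case and the loss of the randomised comparison do not.

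The documents do not show that the restriction is intended, and the EMPOWER-I result points the other way. The primary analysis, its analysis set and its type I error are untouched. This is a defect in a secondary analysis that should be corrected because that analysis is the check on a self-reported outcome.

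**What to change.** Replace the sentence in section 6.0 with:

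> A secondary analysis will include all randomised women. Success is a breast MRI and a mammogram that are both confirmed by imaging report; women without confirmation are counted as not having had the test. The stratified Cochran-Mantel-Haenszel test will be used as for the primary analysis.

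Also report the confirmation rate among self-reporters by arm, and add a sensitivity version that excludes only women whose self-reported tests could not be confirmed and keeps women who reported no imaging.

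Cost: a few sentences and no new data, since the reports are already being requested (sections 5.1 and 5.4). There are two downsides. With 85.7% confirmation in both arms, the difference shrinks from 20 to 17.1 points and power falls from about 93% to about 87% (107 per arm, no continuity correction). And if confirmation is higher in the intervention arms, the estimate is biased toward them. The by-arm rates reveal that bias but do not remove it, so the result must be read alongside them.

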## EMPOWER-II

2.1.1 To determine the effectiveness of PA+PCP compared to PA on breast cancer surveillance rates (breast MRI + mammogram).

2.1.2 To determine the effectiveness of the two interventions on rates of each individual surveillance test: breast MRI or mammography.

2.1.3 To explore moderating and mediating patient and PCP-level factors (from baseline and end-of-study surveys of participants and their PCPs) that predict breast MRI and mammography completion and timing of the obtained surveillance. The 12-month follow-up surveys have been postponed to approximately 18 months to acknowledge the COVID-19 impact on screening availability and feasibility for participants at this time. This change is reflected in all responses regarding the 12-month survey throughout this protocol.

2.1.4 To estimate (1) the replication costs of the interventions and (2) costs resulting from the interventions.

2.1.5a Annotate the repository with sociodemographics of the women, radiation dose/field, and measures of ovarian function, and imaging modality.

2.1.5b Utilize the Mazurowski method of deep learning-based segmentation for normalization of the breast MRIs.

2.1.6 Characterize mammographic breast density, by single-reader radiology review and by semi-manual, semi-automated computer software (Cumulus), in childhood cancer survivors using the breast imaging repository and compare to the mammographic breast density in a cohort of women without a history of cancer and undergoing routine breast mammography, matched 1:3 for age at study, calendar year of mammogram, race/ethnicity, and menopausal status.

2.1.7 Measure BPE on breast MRIs, by single-reader radiology review and by computer-based algorithm, in the repository and compare to a cohort of high-risk women without a prior cancer who are undergoing breast cancer screening with breast MRI; match 1:2 for age at study, calendar year of breast MRI, race/ethnicity, and menopausal status.

2.1.8 Gather exploratory information regarding participant's insurance coverage, cost burdens related to recommended screening practices, and how this burden influences screening engagement.

2.1.9 Explore how participant's past, present, and future screening behaviors may have been impacted by the COVID-19 pandemic, as well as how they have been engaging in telehealth and other alternative options during this time.

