### **3.1 Inclusion Criteria**

Eligible participants will include women who:

- 3.1.1 Participants in the Childhood Cancer Survivor Study (CCSS);
- 3.1.2 Were diagnosed with a childhood cancer prior to the age of 21 years;
- 3.1.3 Were treated with  $\geq 10$  Gy of chest RT (recent revision with a lower dose threshold);
- 3.1.4 Do not have a history of breast cancer;
- 3.1.5 Have not had both a breast MRI *and* mammogram in the previous 24 months;
- 3.1.6 Do not have a contraindication to MRI (i.e., pacemaker);
- 3.1.7 Are 25 years of age or older at time of enrollment;

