## EMPOWER-II

A final attempt to collect study outcomes (mammogram, breast MRI, breast ultrasound, medical records and pathology) from 63 participants who are more than 3 months past the approximated 18-month study window will be done via 2 regular mailings, an email notification (sent by the Duke team), and a follow-up phone call from the CCSS Coordinating Center who will administer the questionnaires over the phone. The mailed packet will include 2 options to complete the end-of-study survey: a) a full survey set or b) an abbreviated version of the survey focusing on the main study outcomes (i.e. were they able to get their breast cancer screening tests done and where). PCP factors will also be collected for this group. This attempt extends this group's participation by up to a year. These participants have already completed the baseline survey but have not responded to multiple automated and email reminders within the initial 18-month study period. This extended timeline will not be applicable to those who are currently active in the study.

To collect information on PCP factors, the Duke team will administer the baseline and end-of-study surveys (print via fax) for the PCPs of the CCSS participants. We will ask women in the baseline survey for the name and contact information for their PCP and will solicit this information via the Eureka app for those who don't have one at baseline.

After completion of the baseline measurement questionnaire, participants will be randomly assigned, in a ratio of 1:1:1, to one of the three groups: control, patient activation (PA), or patient activation + primary care provider activation (PA+PCP). An overview of the 3 groups is presented in **Appendix I**. All participants will receive the mailed education materials used in EMPOWER-I.

Recurring notifications, sent through the Eureka App, will be added to remind participants of pending study activities. Also, a cost sharing survey and a Eureka App user experience survey will be added to the End of Study Questionnaire.

This study will use a 3-group comparative effectiveness design comparing:

- Targeted mailed educational materials (C) including a Survivorship Care Plan;

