Have you had BOTH an MRI and mammogram since receiving your EMPOWER packet or in the last 12 months? -YES -> survey activity: screening -NO ->PCP question and monthly MRI/mammogram reminders (parallel tracks sent 2 weeks between each other)	
IN-APP TEXT: We are happy that you have completed BOTH your breast MRI and mammogram. We have 5 questions for you. Please update your information in the next survey:	
SURVEY ACTIVITY	
When did you get your mammogram?	

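### The exploratory moderator model includes pre-randomisation responses but names no time interaction; with an identity mean and constant moderators, this halves the moderator-by-treatment estimate

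*Combined protocol and SAP*

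**What the plan says.** Section 6.0 (Statistical Analyses) explores moderators with a mixed model, Y = mu(X, alpha, Z, b) + e. The response "is the response vector capturing whether the participant had a breast MRI and mammogram". The design matrix X includes "indicators for treatment group, randomization strata, assessment time (baseline and end-of-study), potential confounders, and moderator variables", so each woman contributes a baseline and an end-of-study response. Random effects and errors are normal with mean zero. No link is given for mu. Whether effectiveness differs by a moderator is to be tested "by including interaction terms between potential moderating variables and the treatment group indicator". No interaction with assessment time is named.

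Five other places bear on this:

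- Section 3.2 randomises women after the baseline questionnaire.
- Criterion 3.1.5 admits women who "Have not had both a breast MRI *and* mammogram in the previous 24 months". A single prior test is allowed, and Section 3.2 stratifies on it.
- Objective 2.1.3 draws candidate factors "from baseline and end-of-study surveys of participants and their PCPs".
- Section 6.1 says that "participants who drop out will be counted as failures in this analysis", meaning the primary analysis. It gives no such rule for the moderator model.
- Section 4.0 describes a last attempt to collect outcomes "from 63 participants who are more than 3 months past the approximated 18-month study window".

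**The concern.** Treatment cannot affect a response that precedes randomisation. If arm terms are not allowed to differ between baseline and end of study, each becomes an average of a true zero and the effect of interest. Objective 2.1.3 asks which factors predict completion of screening, and a reader would take the fitted interaction as the difference in intervention effect between subgroups at end of study. It would not be that quantity.

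The both-tests outcome has a further difficulty. Criterion 3.1.5 makes its baseline value 0 for every woman under any look-back up to 24 months, so those rows carry no information. The plan does not state the look-back for the baseline response. The windows given for both tests are 24 months in criterion 3.1.5 and 12 months in the Appendix II app question ("Have you had BOTH an MRI and mammogram since receiving your EMPOWER packet or in the last 12 months"). The latter is asked after randomisation and does not define the baseline response.

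**Working it through.** The plan gives no figure for this analysis, so there is none to reproduce.

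**Inputs.** From the documents: 320 women, 1:1:1 allocation, control rate 10% (Section 6.2), 63 late responders (Section 4.0). Assumed: a binary moderator at 50%; end-of-study rates of 10% in control at both moderator levels, and 20% and 40% in the intervention arms. The true interaction is therefore 0.20.

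**Algebra, identity mean.** With two rows per woman and covariates constant over time, the random-intercept estimates for treatment, moderator and their product equal those from regressing (Y_base + Y_end)/2 on the same covariates, whatever the within-woman correlation. The expected interaction is

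(delta_base + delta_end)/2 = (0 + 0.20)/2 = 0.10,

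with delta_base = 0 because of randomisation. This step does not use criterion 3.1.5.

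**Both tests, all baseline responses 0.** The variance of the woman's mean is Var(Y_end)/4, so the standard error also halves. Simulation (1,500 trials; listed terms against end-of-study regression):

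| End-of-study data | Interaction (SE), listed terms | Interaction (SE), end of study only | Ratio | 95% coverage |
|---|---|---|---|---|
| Complete | 0.101 (0.058) | 0.202 (0.112) | 0.50 | 61% vs 97% |
| 63 counted as failures | 0.080 | 0.160 | 0.50 | not reported |
| 63 left missing | 0.087 (0.057) | 0.197 (0.126) | 0.44 | 50% vs 96% |

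The coverage can be checked by hand. The interval reaches 0.20 when the estimate exceeds 0.20 - 1.96 x 0.058 = 0.086. With mean 0.101 and SE 0.058 the probability is Phi(0.015/0.058) = Phi(0.26), about 0.60. Repeat runs gave 58% to 61%.

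The third ratio follows from row counts. The random-intercept variance is estimated as 0 in nearly every dataset, so the ratio is end-of-study rows over all rows: 257/(257 + 320) = 257/577 = 0.445.

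With complete data, the mean z is 1.76 against 1.81. Rejection is about 41-43% against 42-45%.

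**Baseline responses that vary.** Their variance enters the woman's mean, so the standard error no longer halves while the estimate still does.

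- Both tests, look-back beyond 24 months, 10-30% positive at baseline (assumed): ratio 0.50-0.51, rejection 21-29% against 42-45%.
- Single test (assumed prior imaging 30-50%, that test 30-80% of it, control 25%): 0.10 against 0.20, power 17-26% against 32-35% for an end-of-study model with that test's baseline status as covariate.

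**Moderator entered at its current value.** With stable prevalence the ratio stays 0.50. With prevalence rising 10-30 points (assumed) it is 0.53-0.83, because the interaction absorbs part of the omitted treatment-by-time effect. With no true interaction, a 20-point treatment effect and a rise in all arms, the listed test rejects in 4.8% (10-point rise), 8.4% and 10.2% (two 20-point cases) and 18.2% (30 points), against 3.4-4.1% for end-of-study data.

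**Logit mean, both tests.** The interaction is not halved (1.012 either way in simulation). Because every baseline response is 0, the time coefficient diverges (24.8, SE 11,494 in one fit). The baseline rows then add nothing, leaving one binary response per woman. Rates of 10% and 30% fit equally well with a subject-specific odds ratio of (0.30/0.70)/(0.10/0.90) = 3.9 at random-intercept SD 0, 7.6 at SD 2, or 14.1 at SD 3. The random-intercept variance is at best very weakly identified.

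**The case against.** The strongest reply is that the plan does not commit to the model that halves. The mean function is general, and additive normal errors do not by themselves make it the identity. The design matrix is said to include the listed terms, so a time interaction is unnamed rather than excluded. Both points stand. They make the halving conditional, and they show that the text leaves the fitted model open. A logit mean removes the halving but leaves a time effect that cannot be estimated for the both-tests outcome.

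A second reply is that Section 6.0 promises tests, not effect sizes, and that in the leading case the test is nearly unchanged. That is right, and it limits the harm there to any estimate or interval that is reported. It does not cover responses that vary at baseline, where power falls.

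Third, several scenarios rest on assumptions. Nothing says that moderators enter at their end-of-study values: objective 2.1.3 covers mediators as well, which Section 6.0 handles separately. The 63 women are the target of a further collection attempt, so leaving all 63 missing is a worst case among them. The single-test case relies on a later sentence of Section 6.0 about having either test, since the response itself is defined as both.

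A reader might also infer that criterion 3.1.5 causes the halving. It does not: the ratio stays at 0.50-0.51 when 10-30% are positive at baseline. The cause is arm terms not crossed with time.

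**Conclusion.** The concern holds in a limited form, and the defect is minor. If the mean is the identity and moderators are constant over time, following the listed terms gives a moderator-by-treatment estimate about half the end-of-study value (about 0.44 of it with 63 responses missing). With all both-tests baseline responses at 0, interval coverage is about 60% for a true 20-point interaction. Eligibility adds only that, for look-backs up to 24 months, the both-tests baseline rows carry no information. In that case the test is essentially preserved; where baseline responses vary, power falls as well.

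Three stronger readings are not supported:

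- That the moderator tests are invalid in general. False positives rise clearly only for a current-value moderator whose prevalence increases by roughly 20 points or more, which is an assumption.
- That the plan necessarily halves the effects. No link is stated and time interactions are not excluded.
- That the trial's main conclusions are at risk. The primary and individual-test Cochran-Mantel-Haenszel analyses do not use this model, and objective 2.1.3 is exploratory.

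**What to change.** Reword the moderator paragraph of Section 6.0:

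- **Both tests:** fit a binomial regression to the end-of-study response on treatment, randomisation strata, moderator and treatment by moderator, with no baseline response rows and no subject random effects.
- **Single tests:** do the same with baseline status of that test as a covariate. Alternatively, keep the repeated-measures model with a binomial distribution, add explicit treatment-by-time and moderator-by-treatment-by-time terms, and test those.
- **In both cases:** use baseline moderator values, state the link, and state how missing end-of-study responses are handled in this analysis. If baseline responses are used, state their look-back.

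The cost is SAP wording only. The both-tests model becomes simpler, the candidate moderators stay the same, no new data are needed, and the primary analysis does not change.
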